1.6 Dose Rationale:

Phase I: Patients with AH and MELD score 11-20

Cohort	N	F-652
1 (MELD 11-20)	3	10 ug/kg
2 (MELD 11-20)	3	30 ug/kg
3 (MELD 11-20)	3	45 ug/kg

Patients will initially be enrolled on dose level 1. At any dose level, three (3) patients will be treated. If no dose-limiting toxicity (DLT) is observed, the next cohort of three (3) patients will be treated at the next higher dose level. If 1 of the 3 patients demonstrates DLT in a given dose level, an additional 3 patients will be treated at that dose level. If only 1 of the 6 patients demonstrates DLT, the next cohort of three patients is entered at the next dose level. If 2 or more of the 6 demonstrate DLT at that dose level, we will deescalate to one dose level lower. At subsequent dose levels, the maximum tolerated dose (MTD) is defined as the dose level where no more than 1 of 6 patients experiences DLT.

Dose escalation will occur only when all patients in the given cohort have completed the 42 or 56 days follow up and PK/PD data are available. The MTD will be based on DLT in the first cycle, and the ability to receive at least 70% of the target dose in cycle 2.

CONFIDENTIAL

This material is the property of the Mayo Clinic. Do not disclose or use except as authorized.

Phase II: Patients with AH and MELD score 21-28

Cohort	N	F-652
1 (MELD 21-28)	3	10 ug/kg
2 (MELD 21-28)	3	30 ug/kg
3 (MELD 21-28)	3	45 ug/kg

In the second phase, once safety of the drug in patients with MELD scores 11-20 has been demonstrated, patients with AH as defined by criteria listed earlier and MELD scores 21-28 will be studied. Dose escalation in these patients will follow the identical format to the Phase 1 of the study as described earlier. That is, in patients with MELD scores 21-28, the initial dose will be 10mcg/kg in 3 patients followed by 30mcg/kg, and ultimately 45 mcg/kg. Finally, we will test a 3rd dose of the maximum tolerated dose at Day 14 (10mcg/kg, 30 mcg/kg, or 45mcg/kg dose) – dose expansion cohort (see below).

Dose Expansion cohort:

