1.8 Population

Patients with alcoholic hepatitis that will be recruited for this study should meet the following criteria:

CONFIDENTIAL

This material is the property of the Mayo Clinic. Do not disclose or use except as authorized.

- a. History of heavy alcohol abuse use: >40 g/day in females and >60 g/day in males for a minimum period of 6 months
- b. Consumed alcohol within 6 weeks of entry into the study
- c. Serum bilirubin > 3mg/dL AND AST >ALT, but less than 500 U/L
- d. MELD score range between 11-28. Patients with MELD scores 11-20 will be included in the first phase and patients with MELD scores 21-28 will be recruited for the second phase and escalation phase.

Patients with alcoholic hepatitis will be enrolled at approximately six clinical sites in the US. Additional sites may be added later to help accrual. The target number of participants to complete the study is 18 (see below).

STUDY NUMBERS:	
Phase I (MELD scores 11-20):	3+3+3 = 9
Phase II (MELD scores 21-28):	3+3+3 = 9
TOTAL participants:	18

Expected duration of patient participation is as follows:

Time expected for all patients to be enrolled:

- Approximately 3 years

Duration of individual patient participation:

- Up to 56 days (3 days Screening, 7-17 days of treatment, Follow up for 42 days following first dose)
- In the Dose Expansion Cohort, subjects receive 3 doses at approximately 7 day intervals. The duration of follow up will be for 56 days following first dose, or 42 days following third dose.

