7.1 Statistical Methods

Primary endpoint (safety): The number and percentage of patients with SAE and increase in MELD score > 5 up to Day 56 following administration of first dose of study drug will be summarized by each dose level. Ninety-five percent confidence interval of the percentage will be calculated too.

Summary of adverse event will also be provided by each dose level.

Secondary endpoint: Pharmacokinetics (PK) and pharmacodynamics (PD) of F-652 in patients with alcoholic hepatitis at the first dose level (10ug/kg) and subsequent dose levels will be determined by the study sponsor using standard pharmacological tools. The total exposure (area under the curve), maximum serum concentration, time at maximum concentration, last measurable serum concentration, time at last measurable concentration, clearance, volume of distribution, elimination half-life, accumulation ratio and dose proportionality will be calculated.

Efficacy signal endpoint: The main efficacy end point is the reduction of AST/ALT or serum triglycerides. If patients show a reduction of AST/ALT or serum triglyceride by 30% at day 42, the drug shows efficacy in this patient. We will calculate the percentage of patients with efficacy (rate) and its 95% confidence interval for each dose level.

We will also use the proportion of patients with 30% change of AST, ALT from baseline to Day 3, Day7, Day14, Day 28, Day 42 and Day 56 as the dependent variable, dose level and baseline AST, ALT and other patients' characteristic at baseline as the covariates to evaluate the change (efficacy) or drug by dose level. A random intercept will be included for accommodating the correlation among the repeated measurement.

Other efficacy endpoints: Paired t-test or signed-rank test will be used to compare the level Lille score. Linear mixed-effect models will be used to analyze the MELD score, triglycerides, CRP, and SAA1 in a similar way to the AST/ALT.

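### Section 7.1 summarises safety and response by dose level and names no MELD stratum, although the two strata are escalated separately over the same doses

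*Combined protocol and SAP*

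**What the plan says.** Section 7.1 uses one summary unit throughout. The primary safety measure (SAEs and a MELD rise of more than 5), with its 95% confidence interval, "will be summarized by each dose level". For adverse events: "Summary of adverse event will also be provided by each dose level". For response: "We will calculate the percentage of patients with efficacy (rate) and its 95% confidence interval for each dose level". The repeated-measures model for AST and ALT takes "dose level and baseline AST, ALT and other patients' characteristic at baseline as the covariates", and MELD, triglycerides, CRP and SAA1 are to be modelled in a similar way. Neither phase nor MELD stratum is named in any of these.

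The design has two strata. Section 1.8: "Patients with MELD scores 11-20 will be included in the first phase and patients with MELD scores 21-28 will be recruited for the second phase". Section 1.6 repeats the whole escalation in the second stratum: "Dose escalation in these patients will follow the identical format to the Phase 1 of the study as described earlier", and "the initial dose will be 10mcg/kg in 3 patients followed by 30mcg/kg, and ultimately 45 mcg/kg". MELD 21-28 patients are entered only after safety has been shown in MELD 11-20.

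**The concern.** Each dose is given in two cohorts of different disease severity, and the design treats them as separate safety questions. A table with one column per dose does not show the result in the more severe stratum, which the second phase exists to obtain.

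There is also a confounding risk. The 3+3 rule can add patients to a cell, or stop escalation in one stratum before the other. The severity mix then varies by dose. If the event risk also differs between strata, the crude rate by dose changes even when dose has no effect. The same holds for the response rate.

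**Working it through.** **Inputs from the protocol.** Sections 1.6 and 1.8: two strata, three doses, three patients per cell, so 2 × 3 × 3 = 18, which matches the stated total. Section 1.6: three more patients at a dose after one DLT in three, and, under the Dose Expansion heading, six more at the MTD if only one of three responds. The protocol gives no event risk by stratum, so the risks below are assumptions. The plan gives no figure of its own on this point.

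**Step 1: what dose level means in 7.1.** The pharmacokinetic paragraph of 7.1 identifies the first dose level with 10 µg/kg. On that usage a dose level is a µg/kg dose, each dose has two cohorts, and a summary by dose level combines them.

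**Step 2: masking.** Exact (Clopper-Pearson) 95% intervals:

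| Events | Rate | 95% CI |
|---|---|---|
| 0/3 | 0% | 0 to 70.8% |
| 2/3 | 66.7% | 9.4 to 99.2% |
| Pooled 2/6 | 33.3% | 4.3 to 77.7% |

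The pooled line loses the contrast. The stratum intervals are very wide and overlap heavily, so the counts are what the split adds.

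**Step 3: spurious pattern.** With n_L and n_H patients at a dose and stratum risks p_L and p_H that do not depend on dose, the expected crude rate is (n_L·p_L + n_H·p_H)/(n_L + n_H). For 10% and 40%:

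- 3 low, 3 high: (0.3 + 1.2)/6 = 25%
- 6 low, 3 high: (0.6 + 1.2)/9 = 20%
- 3 low, 6 high: (0.3 + 2.4)/9 = 30%
- 9 low, 3 high: (0.9 + 1.2)/12 = 17.5%
- 6 low, 6 high: (0.6 + 2.4)/12 = 25%
- 3 low, 0 high (high stratum stopped earlier): 10%

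Other assumed risks:

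| p_L / p_H | 3+3 | 6+3 | 3+6 | 9+3 |
|---|---|---|---|---|
| 10% / 30% | 20.0% | 16.7% | 23.3% | 15.0% |
| 20% / 50% | 35.0% | 30.0% | 40.0% | 27.5% |

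With equal risks in the strata the rate is the same for every mix.

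**Step 4: how often the mix becomes unequal.** The 3+3 rule was simulated in each stratum (40,000 runs) with DLT risk flat over dose. Assumptions: two or more DLTs in the first three stop escalation; no six-patient expansion; runs in which MELD 11-20 stopped at its first dose are left out. The share of MELD 21-28 patients differed between doses in 77% of trials at 10%/10%, 91% at 5%/25%, 94% at 10%/30% and 97% at 10%/40%. Expected crude rates at 10, 30 and 45 µg/kg were 20.9, 17.3 and 14.8% for 10%/30%, and 26.3, 17.9 and 13.2% for 10%/40%. This is a downward pattern with no dose effect, caused by earlier stopping in the higher-risk stratum.

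**The case against.** Pooling is inferred, since 7.1 never says that the phases are combined. Section 1.6 uses dose level inside one phase's escalation, so by dose level could mean by cohort within phase. That reading is possible but less natural, given how 7.1 itself uses the term. The ambiguity is itself a reason to state the unit.

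A reader might infer that the plan will produce a false dose trend. The documents do not support that. Three patients per cell, or equal expansion in both strata, give the same mix at every dose and no pattern. Both an unequal mix and different stratum risks are needed. The risks are assumed, and nothing in the documents shows that a MELD rise of more than 5 depends on baseline MELD.

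A reader might also infer a rise to 32.5% at the MTD, from three low and nine high: (0.3 + 3.6)/12. But the six-patient rule in 1.6 follows directly on a sentence about phase I, which is MELD 11-20. On that reading the mix is nine low and three high and the rate falls to 17.5%, although the paragraph is loosely written. Nor is the third-dose rule shown to add patients: the count in 1.8 stays at 9 + 9 = 18.

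It would be too strong to say that toxicity is hidden. DLT decisions are made cohort by cohort, the DSMB reviews data every six months, and all data are listed. Nor is stratum excluded from the models, because unnamed baseline characteristics are allowed. Finally, the Study Summary promises a separate, more detailed SAP. That can carry the fix but does not show that it has been made. The response review by cohort in 1.6 covers phase I only and does not address safety.

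**Conclusion.** The point holds in a limited form. Section 7.1 fixes dose level as the summary unit for the primary safety endpoint, adverse events and response, names no MELD stratum, and on its plain reading merges two separately escalated groups.

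The summary tables can therefore mask a stratum contrast. They can also show a spurious dose pattern in either direction if the mix becomes unequal and the stratum risks differ. Under the assumed 10%/40% risks, a true flat 25% moves to between 17.5% and 30% for the 6+3, 3+6 and 9+3 mixes, and to 10% where the higher stratum contributes no patients. An unequal mix is likely once the 3+3 rules operate (77 to 97% of simulated trials); a difference in stratum risk is an assumption.

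Escalation decisions and listings are not affected. The weakness is in the reported summaries, and correcting it costs almost nothing.

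**What to change.** In 7.1, or in the SAP with 7.1 aligned to it:

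- Report the primary safety endpoint, adverse events and response rate by dose level within MELD stratum (11-20, 21-28), as counts and percentages with exact 95% intervals for the primary endpoint, adverse events and response. Section 1.9 already specifies an exact interval for response.
- Keep the pooled dose-level figure as a secondary line, labelled as combining both strata.
- Name MELD stratum, or baseline MELD, among the baseline covariates of the repeated-measures models.

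This is a free improvement. It needs extra table columns and one named covariate, with no more patients, visits or data. Cells of three are imprecise, so the text should say that the counts carry the information.

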We define response to the study drug as a decrease in the AST/ALT or serum triglycerides by 30% or more from baseline to Day 42 or Day 56. We will evaluate the patients' response rate for each cohort in phase I. If at the MTD level, the response rate is seen in only 1 of the 3 patients, an additional group of 6 patients will be recruited and treated at the MTD dose level. If efficacy signals can yet not be demonstrated in 2 or more of the 6 patients, the drug will be deemed ineffective. If efficacy signals are demonstrated at the highest safe dose, patients in the final cohort will be administered a third dose (10mcg/kg, 30 mcg/kg, or 45mcg/kg) of the MTD on Day 7 (± 3 days) following the second dose to determine if efficacy can be increased with additional dosing.

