1.9 Power Calculation

As the primary outcome is observational, we have powered this study based upon the efficacy outcome, which is defined as a biochemical signal for success if AST/ALT is reduced by at least 30% on treatment. With no treatment, approximately 15-20% of patients reach this outcome following study drug treatment. We anticipate that a minimum of 50% will achieve this outcome. Using a conservative 2-sided assessment of superiority (50% with outcome vs. 20%), we will require 22 subjects to reach 80% statistical power.

For our efficacy outcome of AST/ALT, our primary analysis will assess a binary outcome of at least 30% reduction when on treatment. We will evaluate this with a 95% confidence interval of the percentage of subjects who have at least 30% reduction in AST/ALT on treatment, using an exact binary confidence interval. As a secondary analysis, we will use

CONFIDENTIAL

This material is the property of the Mayo Clinic. Do not disclose or use except as authorized.

robust linear regression with the change in AST/ALT at follow-up as compared to baseline as the outcome variable and baseline AST/ALT as the predictor. We will pair this analysis with a Bland-Altman plot. The goal of the secondary analysis is to assess the degree to which the reduction in AST/ALT attributable to treatment changes according to the subject's baseline AST/ALT. We will use 2-sides 5% type I error rate throughout.

2 *Study Objectives*

Primary:

- Assess the safety and tolerability and find the MTD of F-652 in patients with alcoholic hepatitis as determined by:
 - a. Absence of unexpected serious adverse events and,
 - b. Absence of worsening of alcoholic hepatitis (as determined by increase in MELD score > 5) up to Day 56 following administration of first dose of study drug.

Secondary:

- Determine the pharmacokinetics (PK) and pharmacodynamics (PD) of F-652 in patients with alcoholic hepatitis.

Additional:

- Assess the efficacy signal of F-652 in patients with alcoholic hepatitis as determined by:
 - a. Clinical: improvement in clinical status
 - b. Biochemical: Improvement in liver biochemistry, MELD and Lille scores at days 7, 28, 42 and 56
 - c. Biomarkers of IL 22 activity (CRP, SAA, triglycerides)

2.1 **Trial Design:**

The following study evaluations will be performed during the course of the Screening period (Day -3 to Day 0):

- Signed informed consent

CONFIDENTIAL

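### The main efficacy responder in 7.1 and 1.6 counts AST/ALT or triglycerides, but the only untreated rate, target and sample size (1.9) are for AST/ALT alone

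*Combined protocol and SAP*

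**What the plan says.** Three sections define efficacy success, and they do not agree.

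- **Section 7.1 (efficacy signal endpoint):** "The main efficacy end point is the reduction of AST/ALT or serum triglycerides". At patient level, "If patients show a reduction of AST/ALT or serum triglyceride by 30% at day 42, the drug shows efficacy in this patient". The rate and its 95% confidence interval are reported for each dose level.
- **Section 1.6 (Dose Expansion cohort):** "We define response to the study drug as a decrease in the AST/ALT or serum triglycerides by 30% or more", measured to Day 42 or Day 56. This responder feeds the rule that can declare the drug ineffective, and the judgement that efficacy signals are present.
- **Section 1.9 (Power Calculation):** the efficacy outcome is "defined as a biochemical signal for success if AST/ALT is reduced by at least 30% on treatment". To that outcome 1.9 attaches an untreated rate ("With no treatment, approximately 15-20% of patients reach this outcome following study drug treatment"), a 50% target, 22 subjects for 80% power, and a primary efficacy analysis by exact 95% interval.

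Section 2 lists liver biochemistry and "Biomarkers of IL 22 activity (CRP, SAA, triglycerides") as separate items under the efficacy-signal objective. The Study Summary says efficacy signals are compared with historical patient data.

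**The concern.** An either/or responder succeeds at least as often as either component alone. Adding triglycerides therefore leaves the untreated response rate unchanged or raises it, while the only benchmark in the documents stays at the AST/ALT value. The plan also names two lead efficacy responders: a main endpoint in 7.1 and a primary efficacy analysis in 1.9. Nothing says which is to be read against history, so the choice could be made after the data are seen. In an uncontrolled study, a composite rate set beside a 15-20% AST/ALT rate can look like activity when there is none. The 1.6 rule uses the composite directly, so wherever triglycerides are available it is at least as easy to pass as with AST/ALT alone.

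**Working it through.** **1. Reproduce the plan's figure.** Inputs from 1.9: null 20%, target 50%, two-sided 5%, power 80%. The one-sample normal approximation with variance at the target gives

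(1.960 + 0.842)² × 0.5 × 0.5 / 0.30² = 21.8, rounded up to 22.

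The stated 22 is thus a one-sample figure for the AST/ALT-only outcome.

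**2. Null rate of the composite.** Let a be the untreated AST/ALT response rate and q the untreated triglyceride response rate. The documents give a = 15-20%. They give neither q nor the association between the two responses, so both are assumptions here.

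- Independent: 1 − (1 − a)(1 − q)
- Triglyceride responders nested within AST/ALT responders (needs q ≤ a): a

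With a = 20% and independence:

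- q = 10%: 1 − 0.8 × 0.9 = 28%
- q = 20%: 1 − 0.8 × 0.8 = 36%
- q = 30%: 1 − 0.8 × 0.7 = 44%

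**3. Chance that an inactive drug's exact (Clopper-Pearson) 95% interval lies wholly above 20%.** This is the error that arises if the 7.1 rate is read against 1.9's figure. Section 7.1 reports by dose level, which is 3 patients per dose in each phase, or 6 if both phases are combined. The pooled 18 is the planned total.

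| Patients | Responders needed | True rate 20% | 28% | 36% | 44% |
|---|---|---|---|---|---|
| 3 | 3 | 0.8% | 2.2% | 4.7% | 8.5% |
| 6 | 4 (lower limit 22.3%) | 1.7% | 5.6% | 12.9% | 23.9% |
| 18 | 8 (lower limit 21.5%) | 1.6% | 10.1% | 30.3% | 57.5% |

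**4. Sensitivity to the assumptions.** With a correlation of 0.5 between the two yes/no responses, the composite null is a + q − [aq + 0.5√(a(1 − a)q(1 − q))], or 22/28/35% for q = 10/20/30%. The pooled-18 error is then 2.8/10.1/26.7%. Under full nesting the null stays at 20% and the error at 1.7% (n = 6) or 1.6% (n = 18).

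**5. The 1.6 rule.** The second group of 6 is reached only when exactly 1 of the first 3 responds. Section 1.6 does not say what follows otherwise. I assume that 2 or more of 3 passes directly and 0 of 3 does not. Then

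P(pass) = P(≥2 of 3) + P(1 of 3) × P(≥2 of 6).

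- True rate 20%: 0.104 + 0.384 × 0.345 = 24%
- True rate 28%: 0.191 + 0.436 × 0.536 = 42%
- True rate 36%: 0.295 + 0.442 × 0.699 = 60%

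**6. Are triglycerides available at Day 42?** Section 5.2 lists them at Screening, Day 7, Day 14 (if dosed) and Day 28. The lipid row of the schedule in 2.2 and the Day 42 and Day 56 visit lists in 2.1 also omit them for those two days. The laboratory footnote to the schedule points the other way: it places the lipid profile under serum chemistry, which is drawn on Day 42 and Day 56.

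**The case against.** The strongest reply is that the plan never makes the comparison at issue. Section 7.1 gives a rate and interval by dose level with no benchmark, and 1.6 does not use 20%. In 1.9, where the 15-20% appears, the analysis is on AST/ALT alone and matches its benchmark. This stands. A reader might infer that 7.1 tests the composite against 20% with a false-positive rate of up to 58%, but the documents do not support that. The comparison has to be supplied by whoever interprets the rate, and 58% also needs pooling of all 18 and q = 30% with independence. It remains true that the Study Summary promises comparison with historical data and that 15-20% is the only untreated rate given.

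On most of the schedule, triglycerides are not drawn at Day 42, so the triglyceride limb may never count in 7.1. This also stands as a limit on the consequence, but not as a defence. Either the limb counts and can loosen the endpoint, or the main endpoint cannot be evaluated as written.

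It would also be tempting to say that 1.6 passes an inactive drug 34%, 54% or 70% of the time. Those are the probabilities for the second stage alone and ignore the first 3 patients. The 24% at a true 20% shows that the rule is lax even on AST/ALT alone, and this fix does not change that.

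Nor do the documents place triglycerides outside efficacy. Sections 2, 2.3 and 5.1 all list them among the efficacy signals. Efficacy is an additional objective, and a separate analysis plan is promised. Both points lower the severity.

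**Conclusion.** The mismatch is certain from the text: the responder in 7.1 and 1.6 is not the one to which the untreated rate, target, sample size and primary efficacy analysis in 1.9 apply, and no null rate exists for the composite. The size of the consequence is conditional. It requires that the 7.1 rate be read against 15-20% and that triglycerides be available at the endpoint visit. Under assumed untreated triglyceride response rates of 10/20/30%, independent of AST/ALT, the error rises from 1.7% to about 6/13/24% at 6 per dose level, and from 1.6% to 10/30/58% if 18 are pooled. Positive correlation lowers these figures, and nesting removes the inflation. The 1.6 sequence, completed as assumed above, passes an inactive drug about 24% of the time at a true 20%, 42% at 28% and 60% at 36%. This should be fixed. It does not undermine the primary safety objective.

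**What to change.** Make the responder identical in 1.6, 1.9 and 7.1. The simplest way is to use the AST/ALT-only responder of 1.9 throughout and state that this is the rate to be read against 15-20%. Triglyceride response would then be reported separately, as a further efficacy-signal or biomarker result.

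If the sponsor keeps the composite, the plan should state and justify an untreated rate for it, restate the target and sample size in 1.9 on that basis, and say that the composite is not to be read against the 15-20% AST/ALT rate. The triglyceride sampling days in 2.1, 2.2 and 5.2 would also have to be reconciled with the laboratory footnote. Adding Day 42 lipids without correcting the benchmark would make the inflation fully active.

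For the AST/ALT-only option the cost is wording in 1.6 and 7.1, with no new data. The reported response rate may be lower, because patients who respond on triglycerides alone would no longer count.

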2.2 Study Design/Type

Schedule of Procedures

Safety Assessments	Screening (-72 hrs)	Day 1 (± 1 day)	Day 3 (± 1 day)	Day 7 (± 3 days)	Day 14 (± 3 days)	Day 28 (± 4 days)	Day 42 (± 2 days)	Day 56 ⁶ (± 2 days)
Inclusion/Exclusion Criteria	X	X						
Physical Examination	X			X	X ⁵	X	X	X
Medical/Surgical History	X		X	X	X	X	X	X
Nutritional Assessment	X				X ⁵		X	X
AUDIT and NIAAA Questionnaires	X							
Timeline Followback Questionnaire	X					X	X	X
Vital Signs	X		X		X	X	X	X
Serial Vital Signs		X		X	X ⁵			
Serum Chemistry ^A	X	X	X	X	X	X	X	X
Coagulation ^A	X	X	X	X	X	X	X	X
Hematology ^A	X	X	X	X	X	X	X	X
Serum pregnancy test	X							
Urine pregnancy test		X		X	X ⁵			
Lipid profile, CRP, SAA1, total protein, albumin ^A	X			X	X ⁵	X		
Calculate MELD Score	X	X	X	X	X	X	X	X
Calculate Lille Score				X				
Calculate Maddrey Score	X							
Urinalysis ¹	X							
ECG ²	X			X	X ⁵	X		
Chest X-ray ³	X							
Adverse Events		X	X	X	X	X	X	X
Concomitant Medications	X	X	X	X	X	X	X	X
Study Drug Dosing		X		X	X ⁵			
Pharmacokinetic Sample Collection ⁷		X	X	X	X	X	X	
Immunogenicity Testing ⁸	X				X	X	X	
Biomarkers(blood and urine)	X ⁷			X	X	X	X	X
Confirmation that patient is abstinent from alcohol		X	X	X	X	X	X	X

1. Urinalysis results can be used for Screening if tested within 7 days.
2. ECG results can be used for Screening if tested within 7 days.
3. Chest X-ray results can be used for Screening if tested within 30 days.
4. Day 1, Day 7 and Day 14 labs and testing must be completed prior to dosing.
5. These tests/procedures will occur only on Day 14 if the patient is receiving a 3rd dose at that visit.
6. Day 56 will only occur if the patient received a 3rd dose on Day 14.
7. Biomarkers are optional at Screening.

^AClinical Laboratory Tests

Hematology	Coagulation	Serum Chemistry		Urinalysis	Other
		Liver Function Tests	Other Chemistry		
Complete Blood Count with differential, Platelet count, MCV	PT, INR	AST, ALT, Total Bilirubin, Direct Bilirubin	Sodium, Potassium, Chloride, Bicarbonate, Calcium, Magnesium, Phosphate, Creatinine, BUN, Glucose, Total protein, Albumin, Lipid profile, CRP, SAA1	Specific gravity, pH, Blood, Protein, Glucose, Ketones	β-HCG serum pregnancy test Urine pregnancy test

Blood will be collected for PK sampling per the schedule below:

⁸Pharmacokinetic Sampling Schedule

Study Visit Day					Study Visit Day +0*	Study Visit Day +2*	Study Visit Day +3*	Study Visit Day +4*
					24 hrs	48 hrs	72 hrs	96 hrs

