5.2 Method and Timing

1. MELD score will be calculated at each visit.
2. Lille score will be calculated on Day 7.

CONFIDENTIAL

This material is the property of the Mayo Clinic. Do not disclose or use except as authorized.

3. Triglycerides, CRP and SAA1 will be collected at Screening, Day 7, Day 14 (if dosed) and Day 28.
4. AST and ALT will be collected at Screening, Day 3, Day 7, Day 14, Day 28, Day 35, Day 42 and Day 56 (if applicable).
5. Adverse events will be evaluated at each study visit per the Schedule of Procedures by the study coordinator and reviewed by the investigator

6 *Assessment of Safety*

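### Response can rest on triglycerides at Day 42 or Day 56, but most of the plan ends lipid sampling at Day 28

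*Combined protocol and SAP*

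**What the plan says.** **The response rule.** Section 7.1 states: "The main efficacy end point is the reduction of AST/ALT or serum triglycerides". It then classes each patient: "If patients show a reduction of AST/ALT or serum triglyceride by 30% at day 42, the drug shows efficacy in this patient". Section 1.6 (Dose Expansion cohort) defines response as a "decrease in the AST/ALT or serum triglycerides by 30% or more from baseline to Day 42 or Day 56".

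**What the rule decides.** Section 1.6 adds six patients under this condition: "If at the MTD level, the response rate is seen in only 1 of the 3 patients". It then says: "If efficacy signals can yet not be demonstrated in 2 or more of the 6 patients, the drug will be deemed ineffective". Efficacy signals at the highest safe dose also lead to the third-dose step.

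**When lipids are sampled.** Section 5.2 states: "Triglycerides, CRP and SAA1 will be collected at Screening, Day 7, Day 14 (if dosed) and Day 28". In the Section 2.2 schedule, the row "Lipid profile, CRP, SAA1, total protein, albumin" has its last mark at Day 28. In Section 2.1, the Day 28 list names the lipid profile; the Day 42 and Day 56 lists name only clinical chemistry, hematology and coagulation. Against this, the panel table below the schedule includes "Total protein, Albumin, Lipid profile, CRP, SAA1" under Serum Chemistry, and the serum chemistry row is marked at every visit, including Days 42 and 56.

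**A further responder.** Section 1.9 powers the study on AST/ALT alone, measured on treatment.

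**The concern.** The rule calls for a triglyceride value at Day 42 or Day 56, and most of the sampling text does not provide one. If 5.2 is followed, a patient whose AST/ALT has not fallen by 30% cannot be assessed on the second marker at the stated time. The plan does not say whether that patient is a non-responder or not evaluable. Sites could also read 2.2 differently, so that some hold Day 42 lipids and others do not.

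The stakes come from the small groups. The rule is applied to three patients and then to six, and it decides whether more patients are recruited and whether the drug is called ineffective.

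**Working it through.** **1. The passages side by side**

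| Place | Lipids at Day 42/56? |
|---|---|
| 1.6, response definition | Needed (Day 42 or 56) |
| 7.1, response definition | Needed (Day 42) |
| 5.2, collection times | No; last at Day 28 |
| 2.2, lipid row | No; last at Day 28 |
| 2.1, visit lists | No; last named at Day 28 |
| 2.2, panel table with serum chemistry row | Yes, by implication |
| 15, analyte list | Lipid profile is under Special Investigations, apart from Serum Chemistry |

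The Biomarkers row in 2.2 is also marked at Days 42 and 56, and the objectives name triglycerides as a biomarker of IL-22 activity. The 2.1 lists describe that collection as specimen banking, and nothing says that triglycerides will be assayed on it. AST and ALT are scheduled at Day 42, and at Day 56 where applicable (5.2).

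**2. The plan's own figure**

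Section 1.9 asks for 22 subjects (50% versus 20%, two-sided 5%, 80% power). With the variance under the alternative: (1.960 + 0.842)² × 0.5 × 0.5 / 0.3² = 21.8, rounded up to 22. It reproduces. It concerns AST/ALT only, so the triglyceride gap does not change it.

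**3. One patient can change a decision**

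- Three patients at the MTD: one responds on AST/ALT, one on triglycerides only, one on neither. With triglycerides the count is 2 of 3; without, 1 of 3, and six more are recruited.
- Six further patients: one AST/ALT responder and one triglyceride-only responder. With triglycerides the count is 2 of 6; without, 1 of 6, and the drug is called ineffective.

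**4. Illustration of size**

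Let p be the AST/ALT response rate; 1.9 gives 50% anticipated and 20% as the upper end for untreated patients. Let q be a triglyceride response rate independent of AST/ALT. **q and independence are assumptions; the documents give neither.** Without triglycerides (q = 0), a patient with no AST/ALT fall counts as a non-responder. I take the efficacy signals in the six-patient rule to mean this responder definition and the six to be the additional patients.

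r = 1 − (1 − p)(1 − q)
A = P(exactly 1 of 3) = 3r(1 − r)²
B = P(at most 1 of 6) = (1 − r)⁶ + 6r(1 − r)⁵
Literal path to ineffective in 1.6 = A × B

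| p | q | r | A | B | A × B |
|---|---|---|---|---|---|
| 0.50 | 0 | 0.50 | 0.375 | 0.109 | 0.041 |
| 0.50 | 0.10 | 0.55 | 0.334 | 0.069 | 0.023 |
| 0.50 | 0.20 | 0.60 | 0.288 | 0.041 | 0.012 |
| 0.20 | 0 | 0.20 | 0.384 | 0.655 | 0.252 |
| 0.20 | 0.10 | 0.28 | 0.435 | 0.464 | 0.202 |
| 0.20 | 0.20 | 0.36 | 0.442 | 0.301 | 0.133 |

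The path moves 2 to 3 points at p = 50% and 5 to 12 points at p = 20%. The expansion trigger A falls with q at 50% and rises with q at 20%. If every triglyceride responder is also an AST/ALT responder, r = p and nothing moves.

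**5. A related mismatch: the Lille score**

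Section 7.1 plans a paired test of the Lille score. Sections 2.2 and 5.2 schedule the score only at Day 7, which leaves nothing to pair it with. The Study Summary and Section 2 list Lille at Days 7, 28, 42 and 56.

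**The case against.** **The panel table may govern.** If lipids belong to serum chemistry, Day 42 and Day 56 values will exist. The lipid row is also not a clean guide: it carries total protein and albumin, which Section 15 lists under Serum Chemistry. This stands as far as it goes, and a reader should not infer that late lipids will certainly be missing. But it leaves 5.2, which is explicit, in conflict with the table.

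**The rule is an either/or rule.** AST/ALT can still be assessed at Day 42 and is the only powered outcome; efficacy is an additional objective. All of this stands. It would be wrong to infer that the endpoint cannot be evaluated.

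**The direction is not settled.** A reader might infer that losing triglycerides makes the trial too likely to reject an active drug. The documents do not support that: a second route also admits chance responders, and the largest shifts above occur at 20%, within the plan's untreated range. Section 2.3 also lists efficacy signals more broadly than the 30% rule, so the reading of the six-patient rule is an assumption.

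**A separate SAP is promised.** The Study Summary defers detailed methods to it. It could supply the missing-component rule, but it cannot create a sample that was not taken.

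**Conclusion.** The inconsistency is real and should be fixed. Sections 1.6 and 7.1 use triglycerides at a time when 5.2, the lipid row and the visit lists no longer collect them; the panel table points the other way, and the Biomarkers row appears to be banking only. If 5.2 governs, the triglyceride route cannot be evaluated at its stated time point.

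The effect is limited to the efficacy signal. The primary safety endpoint and the figure of 22 are unaffected. Within that limit, one reclassified patient can change the expansion or the ineffective decision. How often, and in which direction, is unknown; the figures above illustrate an assumed rate and do not estimate an error.

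On Lille, a reader might infer that the paired test is impossible. That follows only if the Day 7 schedule prevails over the objectives. The withdrawal wording in 3.4, 6.1 and 6.9, which refers to Lille scores at any time, is a separate matter and need only be reconciled with the schedule.

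**What to change.** Use one responder definition and one time point in 1.6 and 7.1, and state how they relate to the AST/ALT-only, on-treatment outcome in 1.9. Then choose:

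- **(a) Preferred: keep both markers.** Add the lipid assay to the existing Day 42 draw, and to Day 56 for three-dose patients. Correct 2.1, the lipid row and panel table in 2.2, and 5.2 to match. Cost: one assay on blood already being drawn, plus wording; wording only if the panel table already reflects practice.
- **(b) Otherwise: define response on AST/ALT alone.** Report triglycerides separately through Day 28, and make the panel table agree with the lipid row. Cost: wording only, but the triglyceride route to response is lost, and the size of that loss is unknown.

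Under either option, state in 7.1 how a patient with a missing component is counted. Settle this before any response decision, because an uncollected sample cannot be recovered.

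For Lille, reconcile the Study Summary and Section 2 with 2.2 and 5.2. If only the Day 7 score is kept, replace the paired test with a descriptive summary.
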